8. EFFICACY EVALUATION

8.1 Overview of Efficacy Analysis Issues

The primary objective of this study is to evaluate long-term safety and tolerability of 5% and 15% sofpironium bromide gel. Primary endpoints are safety parameters and are described in Section 9.

Efficacy is of secondary importance for the study; all efficacy endpoints are described below.

8.1.1 Handling of Dropouts or Missing Data

Missing data will not be imputed for any of the efficacy endpoints.

8.1.2 Multicenter Studies

This is a multicenter study, with approximately 30 sites expected to participate. Data collected from all sites will be pooled for data analysis.

8.1.3 Assessment Time Windows

Allowable windows for each study visit are laid out in the Schedule of Events in Section 18.1. Assessments that occur outside of the allowable window for each study visit will be flagged as protocol deviations, but will be used in all analyses. In general, all data will be associated with the nominal study visit for which it was intended. Repeat assessments and unscheduled visits will be included in study listings, but will not be used in place of nominal timepoint data. It is not expected that there will be multiple measurements that occur within the same assessment time window. Should that occur, the closest measurement will be used in the analysis; an earlier measure will be used in case of a tie.

8.1.4 Definitions

For the purposes of analysis, Baseline and End of Treatment (EOT) definitions for HDSM-Ax as well as the other efficacy parameters of interest are defined below.

HDSM-Ax

The HDSM-Ax 11-Item scale (HDSM-Ax-11) will be defined as mean of the items in sections No. 1, 2, and 3 of the HDSM-Ax (11 sub-items in total). This will be applied to both the \geq 12 years of age scale and the child scale. The mean will be derived by taking the total score and dividing by the number of questions answered. Subjects must answer at least 6 of the 11 sub-items to be evaluable for HDSM-Ax-11 total score.

The HDSM-Ax 7-Item scale (HDSM-Ax-7) will be defined as the mean of the items in section No. 1 and questions 2a. through 2e. of the HDSM-Ax (7 sub-items in total). This will be applied to both the \geq 12 years of age scale and the child scale. The mean will be

Version: 1.0 Page 21 of 51

derived by taking the total score and dividing by the number of questions answered. Subjects must answer all of the 7 sub-items to be evaluable for HDSM-Ax-7 total score.

Baseline and EOT values are defined as follows:

- Baseline = Visit 2 (Day 1) assessment
- EOT = Visit 16 (Week 48) assessment

HidroQoL

The HidroQoL is split up into two domains. The Daily Life Activities domain is derived as the sum of questions 1 through 6, and the Psychosocial Life domain is derived as the sum of questions 7 through 18, where the answers are coded as such:

```
"Very Much" = 2
"A little" = 1
"No, not at all" = 0
```

The HidroQoL total score is derived as the sum of the 2 domain scores (range 0 to 36).

DLQI

The DLQI total score is calculated by summing answers to questions 1 through 10, including both parts of Question 7. All questions must be answered at the first DLQI assessment. Subsequent DLQI assessments with a single missing answer will be scored 0 for that question and totaled. Subjects with more than one missing question will have the instrument dropped for that visit. The DLQI answers are coded as such:

```
"Very much" = 3

"A lot" = 2

"A little" = 1

"Not at all" = 0

"Not relevant" = 0

Question 7, 'prevented work or studying' = 3
```

The DLQI is calculated by summing the score of each question resulting in a maximum of 30 and a minimum of 0. The higher the score, the more quality of life is impaired.

PGI-S and **PGI-C**

PGI-S will be defined as Question #6 of the HDSM-Ax at each assessment. PGI-C will be defined as Question #7 of the HDSM-Ax at the Day 43 visit only.

Version: 1.0 Page 22 of 51

8.2 Secondary Efficacy Endpoints

The following secondary efficacy endpoints will be analyzed:

- The proportion of subjects achieving ≥1-point improvement in HDSM-Ax-11 (11-item total) from baseline to end of treatment
- The proportion of subjects achieving ≥1.5-point improvement in HDSM-Ax-11 from baseline to end of treatment
- The proportion of subjects achieving ≥2-point improvement in HDSM-Ax-11 from baseline to end of treatment
- Change of HDSM-Ax-11 from baseline to end of treatment as a continuous measure

8.2.1 Other Efficacy Endpoints

The following other efficacy endpoints will be analyzed:

- The proportion of subjects achieving ≥1-point improvement in HDSM-Ax-7 (7-item total) from baseline to end of treatment
- The proportion of subjects achieving ≥1.5-point improvement in HDSM-Ax-7 from baseline to end of treatment
- The proportion of subjects achieving ≥2-point improvement in HDSM-Ax-7 from baseline to end of treatment
- Change of HDSM-Ax-7 from baseline to end of treatment as a continuous measure
- The proportion of subjects achieving ≥1-point improvement in the HDSM-Ax-11 score from baseline to each of Visits 2-15 and 17 (Weeks 2-44 and Week 52)
- The proportion of subjects achieving ≥1.5-point improvement in the HDSM-Ax-11 score from baseline to each of Visits 2-15 and 17 (Weeks 2-44 and Week 52)
- The proportion of subjects achieving ≥2-point improvement in the HDSM-Ax-11 score from baseline to each of Visits 2-15 and 17 (Weeks 2-44 and Week 52)
- Change in HDSM-Ax-11 from baseline to each of Visits 2-15 and 17 (Weeks 2-44 and 52) as a continuous measure
- The proportion of subjects achieving ≥1-point improvement in the HDSM-Ax-7 score from baseline to each of Visits 2-15 and 17 (Weeks 2-44 and Week 52)
- The proportion of subjects achieving ≥1.5-point improvement in the HDSM-Ax-7 score from baseline to each of Visits 2-15 and 17 (Weeks 2-44 and Week 52)
- The proportion of subjects achieving ≥2-point improvement in the HDSM-Ax-7 score from baseline to each of Visits 2-15 and 17 (Weeks 2-44 and Week 52)
- Change in HDSM-Ax-7 from baseline to each of Visits 2-15 and 17 (Weeks 2-44 and 52) as a continuous measure
- DLQI from baseline to each of Visits 5, 10, and 16 (Weeks 2, 6, 24, and 48)
- PGI-S summarized as frequency counts and percentages for each category (none, mild, moderate, severe, very severe) at each assessment, change from baseline as a 5x5 table with frequency counts and percentages at each post-baseline assessment

Version: 1.0 Page 23 of 51

• PGI-C summarized as frequency counts and percentages for each category (very much better, moderately better, a little better, no change, a little worse, moderately worse, very much worse) at Visits 10 and 16 (Weeks 24 and 48)

8.2.2 Exploratory Efficacy Endpoints

Exploratory efficacy endpoints to be analyzed include the following:

• HidroQoL from baseline to each of Visits 3 and 5 (Weeks 2 and 6); only the first 100 subjects ≥ 17 years of age enrolled in the study were to complete this assessment, and an exploratory analysis was performed.

8.3 Analysis Methods

All secondary and other efficacy endpoints will be summarized using descriptive statistics by treatment group for the ITT and PP populations. For continuous measures, mean, standard deviation, median, minimum and maximum will be reported for results at time point and for change from baseline by visit as indicated in Section 8.2.1. For categorical measures, frequency and percentage of subjects will be reported by the visits indicated in Sections 8.2 and 8.2.1. The exploratory HidroQoL endpoint will be summarized by treatment group as a continuous measure using descriptive statistics. At each visit, both domain scores and the total score will be summarized for the HQL population. No formal hypothesis testing or modeling of efficacy endpoints will be performed. Figures for proportion of subjects achieving ≥1-point, ≥1.5-point, and ≥2-point imprpovment in HDSM-Ax (for both 7-Item and 11-Item) by visit will be provided. Additionally, figures of mean change from baseline over time for HDSM-Ax (for both 7-Item and 11-Item) will be provided.

Version: 1.0 Page 24 of 51

9. SAFETY EVALUATION

9.1 Overview of Safety Analysis Methods

All safety data will be analyzed and presented by treatment received for the Safety Population.

9.1.1 Handling of Dropouts or Missing Data

All available information will be used for descriptive statistics. No imputation for missing data will be applied with the exception of the handling of partial dates.

Partial AE and concomitant medication start and end dates will be imputed as follows:

- 1. If the year and month are known:
 - a. If the year and month are the same as the year and month of the treatment start date, impute to treatment start date and will therefore be recorded as TEAEs.
 - b. Otherwise, use the 1st of the month.
- 2. If only the year is known:
 - a. If the year is the same as the year of treatment start date, impute to treatment start date and will therefore be recorded as TEAEs.
 - b. Otherwise, impute to January 1st of that year.
- 3. If the date is completely missing, impute to treatment start date.

Listings will show the actual dates collected and not the imputed dates.

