9.4 Adverse Events

Treatment-emergent adverse events (TEAEs) are defined as those adverse events (AEs) with onset after the first dose of study drug or existing events that worsened after the first dose during the study. Treatment-emergent AEs will be summarized by treatment group. Partial or missing start or end dates will be imputed per Section 9.1.1.

Verbatim terms on case report forms will be mapped to preferred terms and system organ classes using the latest version of MedDRA.

At Weeks 2, 4, 6, 12, 24, 48 and 52, treatment-emergent adverse events (TEAEs, i.e., AEs occurring during or after treatment initiation) will be summarized in the following tables: all reported TEAEs, all treatment-related TEAEs, severe TEAEs, TEAEs leading to dose interruption, TEAEs leading to dose modification, TEAEs leading to study discontinuation, TEAEs of special interest, and anticholinergic TEAEs. Two sets of the above tables will be produced: (a) for cumulative TEAEs up to the current visit reported by those making the visit, and (b) for cumulative TEAEs up to the current visit reported by all Safety Population subjects (including those absent from the current visit). At each of the 7 indicated weeks, each of the above tables will summarize the subject incidence (frequency count and %) for the specified TEAE, mapped to MedDRA System Organ Class and Preferred Term, according to the highest severity reported. Subjects with only unknown severity for a TEAE will be counted under the severity unknown category. Additionally, serious TEAEs and treatment-related serious TEAEs will be summarized in the same manner for all data through Week 52.

Version: 1.0 Page 26 of 51

Summaries that are displayed by system organ class and preferred terms will be ordered by descending incidence of system organ class in the combined BBI-4000 group and preferred term within each system organ class. The combined BBI-4000 group will not be displayed and will only be used for sorting. TEAEs of special interest include the following:

- Vision blurred
- Mydriasis
- Urinary hesitation
- Pupils unequal

Adverse event data will be presented in data listings by subject, treatment group, and event. Serious TEAEs and TEAEs leading to discontinuation of the study will be presented in separate data listings. Death is not expected. However, should death occur on study, the event will be reported with detailed narratives.

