9.7.3 Other Safety Measures

9.7.3.1 Prior and Concomitant Medications

Medications will be coded using the latest version of the WHO drug dictionary. Medications entered on the CRF will be mapped to ATC drug class (level 4) and drug name.

Prior and concomitant medications will be summarized separately and the study phase of each medication will be determined programmatically based on medication start and end dates. Partial or missing start and end dates will be imputed according to Section 9.1.1.

A prior medication is defined as any medication administered prior to the date of the first dose of study drug. A concomitant medication is defined as any medication administered

Version: 1.0 Page 28 of 51

Statistical Analysis Plan 24 February 2020

on or after the date of the first dose of study drug. A medication may be defined as both prior and concomitant.

For the summary of both prior medications and concomitant medications, the number and percentage of subjects receiving any medication will be summarized by treatment group, as will the number and percentage receiving any medication by ATC drug class and generic drug name. Subjects reporting use of more than one medication at each level of summarization (any medication received, ATC class, and generic drug name) will be counted only once. ATC class terms will be displayed by descending order of incidence, as will generic drug names within each ATC class. The study phase during which each medication was received (e.g., prior, concomitant, or both) will be presented on the listing of prior and concomitant medications.

Prior or concomitant therapies and procedures will be listed only.

Version: 1.0 Page 29 of 51

Statistical Analysis Plan 24 February 2020

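### The SAP's date-imputation rule ignores recorded end dates, so some adverse events that ended before first dose count as treatment-emergent and some medicines leave the prior-medication table

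*SAP*

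**What the plan says.** SAP 9.1.1 opens its list with "Partial AE and concomitant medication start and end dates will be imputed as follows". The list has five branches:

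- **1a.** Month and year known and equal to those of treatment start: "impute to treatment start date and will therefore be recorded as TEAEs".
- **1b.** Any other known month: the 1st of that month.
- **2a.** Only the year known, and equal to the year of treatment start: treatment start, with the same TEAE (treatment-emergent AE) statement as 1a.
- **2b.** Any other known year: 1 January.
- **3.** "If the date is completely missing, impute to treatment start date".

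No branch looks at the other date on the record. The section ends with "Listings will show the actual dates collected and not the imputed dates".

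SAP 9.4 defines TEAEs as "those adverse events (AEs) with onset after the first dose of study drug", or existing events that worsened after it, and then states: "Partial or missing start or end dates will be imputed per Section 9.1.1". SAP 9.7.3.1 says that "the study phase of each medication will be determined programmatically based on medication start and end dates", and also sends incomplete dates to 9.1.1. It defines prior as given before the first-dose date and concomitant as given on or after it, and a medicine may be both. SAP 13 (changes from the protocol) does not mention the rule. The protocol supplied has no date-imputation rule.

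**The concern.** Imputing an unknown AE onset to first dose is a cautious convention when nothing else is known about timing. Here it also applies when the record settles the matter. Protocol 9.2.1 records AEs from informed consent, and Protocol 7 allows consent up to 31 days before Baseline, so events that started and ended before dosing can be in the database. A recorded end before first dose shows that such an event was not treatment-emergent, and the rule discards that evidence. The TEAE tables are the main output for the primary safety objective.

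For medicines the same convention is not cautious, because it removes possible prior use. In this trial certain medicines are allowed only if stable before Baseline (Protocol 4.3), and adding them on study is prohibited (Protocol 6.2). A stable medicine whose start is known only to the year of first dose would be classed as if begun on Day 1. The listing shows the collected dates, but under SAP 9.7.3.1 it also shows the derived phase, so the wrong class appears there too.

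Applying an onset rule to end dates can also give an end that precedes a known onset.

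**Working it through.** The plan gives no figure on this point, so there is none to reproduce. The check applies the five branches as written to constructed records.

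**Inputs.** The rule is from SAP 9.1.1 and the classifications from SAP 9.4 and 9.7.3.1. SAP 2.3 gives 100 and 200 subjects dosed (5% and 15% arms), and SAP 2.6 gives 50 and 100 completers. First dose on 20 Sep 2018 is an assumption for illustration.

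**1. AE recorded as ended 10 Sep 2018**

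| Onset recorded | Branch | Imputed onset | End minus onset | TEAE? |
|---|---|---|---|---|
| Sep 2018 | 1a | 20 Sep 2018 | −10 days | yes |
| 2018 | 2a | 20 Sep 2018 | −10 days | yes |
| missing | 3 | 20 Sep 2018 | −10 days | yes |
| Aug 2018 | 1b | 1 Aug 2018 | positive | no |
| 2017 | 2b | 1 Jan 2017 | positive | no |

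Only 1a and 2a state the TEAE consequence. Branch 3 gives the same date and gets there through the second wording in SAP 9.4, which counts events from treatment initiation onward. Fully dated AEs are unaffected.

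*How often a partial date triggers the rule.* Assume first-dose dates uniform over 2018 and pre-dose onsets uniform over the 31 days before dosing. A missing day alone then moves about 47% of pre-dose onsets to first dose, a missing day and month about 96%, and a wholly missing date 100%. These are shares of incomplete pre-dose onsets, not of all AEs.

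*Effect on the tables.* SAP 9.4 plans tables of "cumulative TEAEs up to the current visit reported by all Safety Population subjects" at Weeks 2, 4, 6, 12, 24, 48 and 52. An onset set to Day 1 enters all seven all-TEAE tables for the full Safety Population (14.3.1.4.2 to 14.3.1.10.2). The most that one subject can add to a row is:

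- full Safety Population: 1/100 = 1.0 percentage point (5% arm), 1/200 = 0.5 (15% arm);
- tables limited to subjects reaching the visit, at the completer target: 1/50 = 2.0 points, 1/100 = 1.0.

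**2. Medicines**

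- Begun 5 Feb 2018, recorded only as 2018, ongoing: the start becomes 20 Sep 2018, 227 days late. It is concomitant only, so it is absent from Table 14.1.5 and present in 14.3.6.4.
- Largest possible shift for this first-dose date: 1 Jan to 20 Sep = 262 days if only the year is known, and 1 Sep to 20 Sep = 19 days if the month is known.
- Start 2018 with end 2018, or start missing with end Sep 2018: both dates become 20 Sep 2018, so concomitant only, even if use was entirely before dosing.
- A medicine with a recorded stop before dosing is not part of this point. SAP 9.7.3.1 uses both dates, so it can still be classed as prior.

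**3. End dates, known onset 15 Mar 2019**

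- End Mar 2019 becomes 1 Mar 2019, 14 days before onset.
- End 2019 becomes 1 Jan 2019, 73 days before onset.
- End missing becomes 20 Sep 2018, 176 days before onset.

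These derived dates are impossible, but no planned table depends on them and listings show collected dates. SAP 3.2 allows similar logic for durations, so the flaw could spread if durations were added.

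**Source of each effect.** Effects 1 and 2 arise because the start rule ignores the end date and applies an AE convention to medicines. Only effect 3 comes from sharing one list between start and end dates.

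**The case against.** The case for leaving the text alone has four parts.

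- *The records are rare.* Screening lasts at most 31 days, health is reviewed at Screening and Baseline, and start and resolution dates are to be documented for each AE (Protocol 9.2.1.2). An exact pre-dose end with an onset known only to the year, or not at all, is implausible; a missing day is the realistic case. This stands and is the main reason the point is minor.
- *The convention is declared and conservative.* SAP 9.4 adopts 9.1.1, which states its consequence openly, and for AEs the error can only add TEAEs. This stands when the end date is unknown, and the fix keeps it. It does not justify counting an event documented as over before dosing.
- *The percentage-point figures are maxima.* A subject who already has a TEAE in the same row does not move it, and the 2.0 and 1.0 figures fit only late reached-visit tables for a subject who stays to the end. This stands. The tables are also descriptive, with no planned tests.
- *Any rule misclassifies some medicines with unknown starts.* This is true, and the medicine still appears in the concomitant table. But SAP 9.7.3.1 allows a medicine to be both prior and concomitant, so possible prior use need not be removed.

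Programmers might add an end-date check unprompted. The SAP does not ask for one, and its medication phase is to be assigned by program.

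**Conclusion.** The concern holds, as a minor point. As written, SAP 9.1.1 can give an AE an onset after its own recorded end and count it as a TEAE, contrary to the definition in SAP 9.4. It also removes from the prior-medication table medicines with an uncertain start that may have begun before dosing. Impossible end dates are a by-product with no effect on planned tables.

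The size is at most 1.0 percentage point (5% arm) or 0.5 (15% arm) per misclassified subject per row, repeated across seven cumulative tables. This rests on the rule being programmed literally and on the planned 100 and 200 subjects dosed. The number of incomplete dates cannot be derived: the documents give no count, and the case report forms are not available. The SAP cites protocol Amendment 4, whereas the protocol supplied is Amendment 01, so the collection rules cited here may have changed.

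**What to change.** Replace the single list in SAP 9.1.1 with three rules.

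1. **AE onsets.** Impute to treatment start only if the end date is missing or could fall on or after first dose. A recorded end before first dose, either a full date or a month or year wholly before it, makes the event not treatment-emergent.
2. **Medicines.** Do not impute partial or missing starts to treatment start. Class as prior any medicine whose start is missing, whose partial start is compatible with a pre-dose date, or whose recorded end is before first dose. Class it also as concomitant if it is ongoing, or if its end is missing or on or after first dose. An end-date check alone is not enough here, because it does not restore medicines that continued past first dose.
3. **End dates.** Use the last day of the known month or year, capped at last contact and never before onset. Leave completely missing ends unimputed.

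The cost is a few lines of SAP text and programming, with no new data. The downside is that some medicines truly started after dosing will also be counted as prior.

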9.1.2 Multicenter Studies

The study will be conducted at approximately 30 clinical sites. Data from the sites will be pooled.

9.1.3 Assessment Time Windows

Safety parameters will be collected according to the schedule of assessments in the Time and Events Table in Section 7 of the protocol (Appendix 18.1). No more/less than 14 ± 3 days may elapse between Visit 2 (Baseline) and Visits 3-6 (Weeks 2-8). No more/less than 28 ± 5 days may elapse between each of Visits 7-16 (Weeks 12-48). The End of Treatment visit may occur within ± 5 days of Week 52 (364 days). Summaries will be presented by planned visits where applicable.

Version: 1.0 Page 25 of 51

9.2 Safety Variables

Primary endpoints include evaluation of the long-term safety and local tolerability of 5% and 15% sofpironium bromide gel when applied topically in subjects with axillary hyperhidrosis. Assessment will include:

- Adverse events
- Local tolerability assessments
- Vital signs (blood pressure, pulse rate, respiratory rate, and temperature)
- Laboratory tests (hematology, chemistry, and urinalysis) and pregnancy testing in FOCBP

9.3 Extent of Exposure

Extent of exposure to study treatment will be summarized for the Safety Population by treatment group. The duration of exposure will be presented in days and summarized using descriptive statistics. Drug (pump) dispensation will be provided in a listing, to include total drug delivered per subject. Each pump will be primed, then weighed, prior to dispensing pumps to subjects. Each pump will be weighed upon return. Total drug delivered will be calculated as the total weight of all pumps dispensed minus the total weight of all returned pumps.

